#### 3.3.4.1 Discontinuation of trial treatment

An individual trial participant will discontinue trial medication if:

- the trial participant wants to discontinue trial treatment. The trial participant will be asked to explain the reasons but has the right to refuse to answer.
- the trial participant develops an AE: •
  - CTCAE Grade 3 or higher and the AE was assessed by the Investigator as related to the trial treatment; OR
  - CTCAE grade 4 or higher regardless of attribution to the trial treatment 0
- the trial participant has repeatedly shown to be non-compliant with important trial procedures and, in the opinion of both the investigator and sponsor representative, the safety of the trial participant cannot be guaranteed as he / she is not willing or able to adhere to the trial requirements in the future.
- the trial participant needs to take concomitant medication that interferes with the safety/efficacy of the investigational medicinal product or other trial treatment (refer to Section 4.2.2.1). If short-term, acute use of a restricted concomitant therapy is required (e.g. 5-7 days of antibiotic treatment for an infection), this will not automatically require discontinuation of BI 685509. Similarly, if a trial participant needs to modify a dose, where only a stable dose is permitted (e.g. NSBBs / carvedilol, statins, anti-viral therapy for HBV), this also will not automatically require discontinuation. In both cases, the Sponsor should be consulted.
- the trial participant meets the criteria for hepatic injury (refer to Section 5.2.6.1.4 and • Appendix 10.2)
- the trial participant has an acute liver decompensation event such as VH, therapyrefractory ascites, overt encephalopathy, or other decompensation event based on Investigator judgement
- trial participants with worsening of their liver function (e.g. increase of Child Turcotte • Pugh score of more than 2 points with clinical evidence of deteriorating liver function in the opinion of the Investigator). Refer to Child-Turcotte-Pugh classification method in Appendix 10.3
- trial participants with a QT or QTcF interval > 500 ms, or an increase of QT or QTcF • of > 60 ms from the pre-dose value at Visit 2 / randomization (baseline). Such cases must be reported as AEs
- the trial participant can no longer receive trial medication for other medical reasons such as surgery, AEs, other diseases

- the trial participant's treatment assignment has been unblended due to an emergency situation
- the trial participant has not successfully completed the dose titration period (i.e. Visit 4), but has persistent AEs or severe effects requiring down-titration of the trial medication (refer to Section 4.1.4.1)
- a female trial participant becomes pregnant. The trial participant will be followed up until birth or otherwise termination of the pregnancy. The data of the trial participant will be collected and reported in the Clinical Trial Report (CTR) until last trial participant last visit and any events thereafter will be reported in the BI Pharmacovigilance (PV) database (refer to Section 5.2.6.2.3)

Trial-specific procedures have also been defined for Investigators to follow in case of increased liver enzymes (AST, ALT, and total bilirubin) after randomisation. For details refer to Section 5.2.6.1.4 and Appendix 10.2 [P09-12413].

In the event of intolerance to BI 685509 after successful completion of the dose titration period at Visit 4 (e.g. persistent AEs despite two down-titrations, or severe effects at any dose), permanent treatment discontinuation should also be considered, based on Investigator judgement (refer to Section 4.1.4.1).

In addition to these criteria, the Investigator may discontinue trial participants at any time based on clinical judgement.

If a trial participant permanently discontinues the trial medication before the last allocated dose, an Early Discontinuation (ED) visit is required ideally within 7 days of discontinuing the medication. An EoS visit should be performed 2 weeks after the ED visit. Refer to Sections 6.2.2.1 and 6.2.3 for further details, including guidance with respect to trial assessments that should be included as part of an ED visit.

Boehringer Ingelheim will closely monitor and medically review all adverse events CTCAE Grade 3 and higher.

Boehringer Ingelheim will pause the enrollment of new patient in the trial and ensure the clinical data is reviewed by the data monitoring committee (DMC) for safety before proceeding with the trial if one of the following occurs:

- 1. more than two patients develop a CTCAE grade 3 or higher in the same category; OR
- 2. two or more patients meet the individual patient stopping criteria related to adverse event

In case of a temporary discontinuation, trial medication (BI 685509) should be restarted if medically justified; refer to Section 4.1.4 for details, including instructions regarding dose adjustments.

If new efficacy / safety information becomes available, Boehringer Ingelheim will review the benefit-risk-assessment and, if needed, pause or discontinue the trial treatment for all trial

participants or take any other appropriate actions to guarantee the safety of the trial participants.

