## 4.1.4 Drug assignment and administration of doses for each trial participant

Trial medication will be dispensed at the investigational sites in accordance with the Flow Chart. At dispensing visits trial participants will be given the appropriate number of medication kits for BI 685509 (range 1-2) depending on the interval between the visits (for further kit details refer to Section 4.1.6). The last dose of BI 685509 will be administered in the evening of the day before the EoT visit.

All trial participants, regardless of the treatment group they are assigned to, will start at Visit 2 on a dose of BI 685509 BID or matching placebo. At Visit 3, 7 days later, and again at Visit 4, a further 7 days after Visit 3, all trial participants will be up-titrated first to a dose of BI 685509 BID or matching placebo, and then to a dose of BI 685509 BID or matching placebo. In this way the blind across treatment groups will be maintained (refer to Table 4.1.4: 1). Trial participants will be informed about the dose titration period and will be made aware that up-titration for BI 685509 is being used. If a trial participant does not tolerate an up-titration, e.g. due to orthostatic dysregulation, the rules in Section 4.1.4.1 must be followed. From Visit 4 onwards, trial participants will continue to receive the maximum dose of 3mg BI 685509 BID (unless a down-titration is required), until reaching the EoT visit 8 weeks after starting the trial medication.

If a trial participant has an AE that, based on Investigator judgement, may be related to BI 685509, the trial medication can either be:

• interrupted (i.e. the trial medication is stopped, and subsequently re-started. The uptitration approach described above is followed.)

OR

• the dose can be reduced (down-titrated) for BI 685509 if the trial participant has successfully completed the dose titration period (i.e. Visit 4).

For further details refer to Sections 4.1.4.1 and 4.1.4.2.

All trial medication assignments, including up / down-titrations for BI 685509 and provision of replacement kits, will be managed through the IRT system. Down-titrations of BI 685509 must not be performed by instructing the trial participant to take less than the two daily doses (refer to Section 4.1.4.1).

Page 46 of 98

Proprietary confidential information © 2023 Boehringer Ingelheim International GmbH or one or more of its affiliated companies

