#### 4.1.4.1 Rules for down-titration in case of intolerance to BI 685509

If a trial participant has an AE that, based on Investigator judgement, may be related to trial medication, the down-titration rules below must be followed. These rules apply if the trial participant has successfully completed the dose titration period (i.e. Visit 4) and is either still taking their final assigned dose of trial medication, or if they have missed  $\leq 3$  consecutive doses. If the trial participant has not successfully completed the dose titration period (i.e. Visit 4), down-titration is not permitted; in case of persistent AEs or severe effects, the trial participant must permanently discontinue treatment (refer to Section 3.3.4.1).

• if the trial participant is receiving BID BI 685509 the dose will be down-titrated one level to 2 mg BID BI 685509

Once down-titration has taken place, no further up-titration will be permitted. If a trial participant continues to have an AE, or a new AE develops, that based on Investigator judgement, may be related to trial medication, a second down-titration will be permitted:

• if the trial participant is receiving BID BI 685509 the dose will be down-titrated to BID BI 685509

Down-titration must not be performed by taking less than the two daily doses or by splitting tablets so that a whole tablet is not taken. Down-titration will be managed through the IRT system (refer to Section 4.1.4). After the successful completion of the dose titration period (i.e. Visit 4), in case of persistent AEs despite down-titration, or severe effects at any dose, permanent treatment discontinuation should be considered (refer to Section 3.3.4.1). Trial participants who are down-titrated will need to return to the investigational site to receive their continuing supply of trial medication, either at the next scheduled visit or via an unscheduled visit.

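### After Visit 4, Protocol Section 4.1.4.1 directs down-titration, and leaves stopping to judgement, for adverse events that Section 3.3.4.1 says must end treatment, and no text says which rule prevails

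*Protocol*

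**What the plan says.** **The mandatory stop.** The list in Protocol Section 3.3.4.1 is phrased as an obligation and has no visit limit. Two of its entries are based on grade. The first covers an event that is "CTCAE Grade 3 or higher and the AE was assessed by the Investigator as related to the trial treatment". The second sets a higher threshold but ignores causality: "CTCAE grade 4 or higher regardless of attribution to the trial treatment". Global Amendment 1 (Section 11.1) records that a health authority requested them.

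**The later text of the same section.** For intolerance after successful titration, including severe effects at any dose, "permanent treatment discontinuation should also be considered, based on Investigator judgement". Further on: "In case of a temporary discontinuation, trial medication (BI 685509) should be restarted if medically justified".

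**Dose-adjustment sections.** For an event that may be related, Section 4.1.4 allows medication to be "interrupted (i.e. the trial medication is stopped, and subsequently re-started", or says that "the dose can be reduced (down-titrated) for BI 685509 if the trial participant has successfully completed the dose titration period". Section 4.1.4.1 makes its down-titration rules binding for a possibly related event once titration is complete, if the participant is still on the final assigned dose or has missed no more than 3 consecutive doses. It then says that "in case of persistent AEs despite down-titration, or severe effects at any dose, permanent treatment discontinuation should be considered". Section 4.1.4.2 sets out how to re-start titration after more than 3 missed consecutive doses, whatever the reason, and names an adverse event as an example.

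None of 4.1.4, 4.1.4.1 or 4.1.4.2 mentions a CTCAE grade.

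**The concern.** The same event can fall under a rule that ends treatment and a rule that lowers the dose. An investigator managing intolerance is likely to turn to Section 4.1.4.1, because it is the section on intolerance. That section points to down-titration first and treats permanent stopping as something to consider.

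What is at stake is mainly safety: continued dosing of a participant whom the rule requested by the health authority was meant to take off treatment. Hypotension is the obvious example, since orthostatic dysregulation is the dose-limiting effect described in Sections 1.2.3 and 3.2.

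There is also a small effect on reporting. The rule followed decides whether a participant appears under events leading to dose reduction or events leading to discontinuation (SAP Section 7.8.1.3). For hypotension or syncope, it also decides whether the secondary endpoint on discontinuation (Protocol Section 2.1.3) is met.

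**Working it through.** No figure in the plan bears on this point, so the check is a comparison of texts.

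**Step 1: one test case through every rule.** Take hypotension of CTCAE grade 3, judged related by the investigator, after Visit 4, in a participant still on the top dose.

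| Text | Trigger met? | Instruction |
|---|---|---|
| 3.3.4.1, mandatory list | Yes: related and grade 3 | Stop |
| 3.3.4.1, later paragraph | Yes, if the event counts as severe | Consider stopping as well |
| 4.1.4.1, down-titration | Yes: possibly related, titration complete | Follow the down-titration rules |
| 4.1.4.1, closing text | Yes, if the event counts as severe | Consider stopping |
| 4.1.4 | Yes: possibly related | May interrupt and re-start, or reduce |
| 4.1.4.2 | Yes, if more than 3 doses are missed | Re-start titration from the first dose |

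The first and third rows cannot both be carried out.

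**Step 2: does this depend on what severe means?** The down-titration part does not. Its trigger is a possibly related event, with no grade attached. The part about considering discontinuation does depend on it. The protocol grades intensity by CTCAE version 5.0 (Section 5.2.6.1.5) but never ties severe effects to a grade. The SAP labels grades 3, 4 and 5 as severe for hypotension only (Section 7.8.1.5). Overlap with the mandatory criterion is therefore the natural reading, but not a defined one.

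**Step 3: before and after Visit 4.** Before titration is complete, 3.3.4.1 and 4.1.4.1 agree that persistent events or severe effects mean permanent discontinuation. After Visit 4, 4.1.4.1 weakens this to consideration. A site could take that contrast as deliberate discretion. The conflict over severe effects is thus confined to the period after Visit 4.

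**Step 4: is there a precedence rule?** Sections 3.3.4.1 and 4.1.4.1 refer to each other, but neither says which governs. The reference from 4.1.4.1 leads to a section that holds both the mandatory list and the discretionary paragraph.

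**Step 5: the interruption route.** Under 4.1.4.1, "Once down-titration has taken place, no further up-titration will be permitted". A re-start under 4.1.4.2 differs: titration begins again, with at least 7 consecutive days on each dose before the next step. With two steps, that is 2 × 7 = 14 days at the least to return to the top dose. Sections 4.1.4 and 4.1.4.2 set no grade limit on this route.

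**The case against.** The best case for the protocol is that the documents, read as a whole, already give the right answer.

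- In Section 3.3.4.1 the discretionary paragraph follows the mandatory list and contains the word *also*. The next paragraph gives the investigator further discretion on top of the listed criteria. The section then reads as mandatory grounds, an added discretionary ground, and general discretion.
- Section 4.1.4 refers temporary interruptions back to 3.3.4.1. Its own wording is permissive, and re-start is conditional on medical justification. A participant who must discontinue is not, on this view, on a temporary interruption.
- The sponsor reviews all events of grade 3 or higher. Enrolment pauses for data monitoring committee review if more than two participants have a grade 3 or higher event in the same category, or if two or more meet the individual stopping criteria related to adverse events. The second trigger depends on meeting the criteria, so the sponsor has to track them whatever the site did with the dose.

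Much of this stands. A reader might infer that Section 3.3.4.1 contradicts itself; the word *also* allows a consistent reading, so the documents do not support that. A reader might also infer that the interruption rules override the stop. They do not say so, and the reference back to 3.3.4.1 points the other way.

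The objection does not cure Section 4.1.4.1. There the word *also* is absent, the down-titration rules are binding rather than permissive, and no grade limit appears. Sponsor review and the enrolment pause act after the event and do not tell a site which instruction to follow.

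**Conclusion.** The point holds as a conflict between Section 4.1.4.1 and the mandatory list in Section 3.3.4.1 for the period after Visit 4, together with the absence of a precedence statement and of a grade limit on interruption and re-start in 4.1.4 and 4.1.4.2. It is a minor safety clarification.

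Its size cannot be calculated. The documents give no rate of related grade 3 or higher events in this population. Section 1.2.3 reports only mild or moderate events among 49 patients with hepatic impairment treated for up to 4 weeks, which suggests that few participants would be affected. No participant finished 8 weeks before the programme was discontinued (SAP Section 4).

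Two stronger conclusions are tempting and not supported:

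- That the efficacy conclusions are compromised. Protocol Section 7.1 plans no hypothesis test, and the effect is on how events are tabulated.
- That the SAP defines severe in the protocol as grade 3 or higher. Its label is a tabulation rule for hypotension in a document dated July 2024; it does not instruct sites.

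The verdict assumes that a site may apply Section 4.1.4.1 as written without reconciling it with the list in 3.3.4.1. The documents do not show that any site did so.

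**What to change.** - In Section 4.1.4.1, and by cross-reference in 4.1.4 and 4.1.4.2, state that down-titration and re-start apply only to adverse events that do not meet the two grade criteria of Section 3.3.4.1.
- State that events meeting those criteria require permanent discontinuation at all visits. The word permanent is worth adding, because the list in 3.3.4.1 does not use it and the section later mentions temporary discontinuation.
- Limit the wording about considering discontinuation, in 3.3.4.1 and 4.1.4.1, to events that do not meet the criteria.
- Allow an immediate temporary hold while grade and causality are being assessed.

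The cost is protocol wording and a notice to sites; the analysis does not change. The downside is possibly a few more mandatory stops, each losing a Week 8 HVPG value, because HVPG is not required at the early discontinuation visit (Section 6.2.2.1). In this trial that loss has no consequence for the reported analysis, since no Week 8 HVPG was collected (SAP Section 4).

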3.3.4.2 Withdrawal of consent to trial participation

Trial participants may withdraw their consent to trial participation at any time without the need to justify the decision.

If a trial participant wants to withdraw consent, the investigator should be involved in the discussion with the trial participant and explain the difference between trial treatment discontinuation and withdrawal of consent to trial participation, as well as explain the options for continued follow-up after trial treatment discontinuation; please see Section 3.3.4.1.

If a patient withdraws consent for further trial participation, no further data will be collected from the respective patient.

Reporting of data of patients who discontinue/withdraw after randomization the active treatment phase is described in Section 7.2.1.

#### 3.3.4.3 Discontinuation of the trial by the sponsor

Boehringer Ingelheim reserves the right to discontinue the trial overall or at a particular trial site at any time for the following reasons:

- Failure to meet expected enrolment goals overall or at a particular trial site
- New efficacy or safety information invalidating the earlier positive benefit-risk assessment; please see Section 3.3.4.1.
- Deviations from GCP, the trial protocol, or the contract impairing the appropriate conduct of the trial
- Further treatment and follow up of trial participants affected will occur as described in Section 3.3.4.1.
- The investigator/the trial site will be reimbursed for reasonable expenses incurred in case of trial termination (except in case of the third reason).

#### 4. **TREATMENTS**

#### 4.1 INVESTIGATIONAL TREATMENTS

The investigational medicinal products in the trial is BI 685509 and placebo to match BI 685509. Boehringer Ingelheim will supply all products.

#### 4.1.1 Identity of the Investigational Medicinal Products

The characteristics of the investigational medicinal products are described in Tables 4.1.1: 1 to 4.1.1:6 below.

#### Table 4.1.1: 1 BI 685509

Substance:	BI 685509	
Pharmaceutical formulation:	Film-coated tablet	
Unit strength:		
Posology:	BID	
Mode of administration:	Oral	

#### Table 4.1.1: 2 BI 685509

Substance:	BI 685509	
Pharmaceutical formulation:	Film-coated tablet	
Unit strength:		
Posology:	BID	
Mode of administration:	Oral	

#### Table 4.1.1: 3 BI 685509

Substance:	BI 685509
Pharmaceutical formulation:	Film-coated tablet
Unit strength:	
Posology:	BID
Mode of administration:	Oral

#### Table 4.1.1: 4Placebo to match BI 685509

Substance:	Placebo to match BI 685509
Pharmaceutical formulation:	Film-coated tablet
Unit strength:	Not applicable
Posology:	BID
Mode of administration:	Oral

Page 44 of 98

Proprietary confidential information © 2023 Boehringer Ingelheim International GmbH or one or more of its affiliated companies

Table 4.1.1: 5Placebo to match H	BI 685509	
----------------------------------	-----------	--

Substance:	Placebo to match BI 685509
Pharmaceutical formulation:	Film-coated tablet
Unit strength:	Not applicable
Posology:	BID
Mode of administration:	Oral

#### Table 4.1.1: 6Placebo to match BI 685509

Substance:	Placebo to match BI 685509
Pharmaceutical formulation:	Film-coated tablet
Unit strength:	Not applicable
Posology:	BID
Mode of administration:	Oral

#### 4.1.2 Selection of doses in the trial and dose modifications

BI 685509 has been tested in a single rising dose trial, a food effect and DDI trial and two MRD trials in male healthy volunteers. Single doses ranged from to the state and multiple doses up to the daily were tested. Overall, BI 685509 was well tolerated except for dose-limiting orthostatic dysregulation. Up-titration and 3 times daily dosing markedly improved the cardiovascular tolerability (refer to the IB [c02778238]).

One phase 1 multiple oral rising dose trial and one phase 2 trial in trial participants with DN have also been completed. Multiple oral doses up to TID were found to be safe and well tolerated. The highest total daily dose of the was achieved following up-titration in 2 steps over 14 days.

An estimated human dose of mg BID is predicted to achieve pharmacologically relevant exposure in trial participants with hepatic impairment [c02778238, n00261471-01]. As is the maximum tolerated single dose, 2 doses BID and BID and BID) is being evaluated in the phase 2 trial 1366-0021 currently, that is conducted in trial participants with CSPH in compensated alcohol-related cirrhosis. These doses have been selected based on safety and PK results from the Phase I MRD hepatic impairment trial (1366-0020). In addition, BI 685509 BID maintenance dose is also being evaluated in 3 trial participants groups (HBV, HCV and NASH) in trial 1366-0029.

In this trial, **BI** 685509 BID maintenance dose will be evaluated in trial participants with CSPH in decompensated cirrhosis due to non-cholestatic liver diseases, with the potential to down-titrate, if not tolerated just as in trials 1366-0021 and 1366-0029

#### 4.1.3 Method of assigning trial participants to treatment groups

After the assessment of all in- and exclusion criteria, each eligible trial participant will be randomised in a blinded fashion to treatment groups according to a randomisation plan in a

1:1 ratio at Visit 2 via an Interactive Response Technology (IRT) system. Refer to Section 7.4 for further details regarding randomisation and access to the randomisation code.

Note that the medication numbers, assigned via the IRT system at each dispensing visit, are different from the trial participant number (which is generated via the IRT system when a new trial participant is registered [screened] in the system).

The Investigator (and relevant designated site personnel) will be provided with instructions to access the IRT system.

